***Recruitment.*** Subjects for the Aim 1 Pilot and the Aim 2 intervention trial will be recruited using existing NYARWEK peer networks, snowballing and venue-based referrals. All interested and potentially eligible subjects identified by the NYARWEK team will be given a business card of

the NYARWEK peer facilitator they were in contact with and referred to the *Anza Mapema* clinic for eligibility screening.

Enrolment targets are presented in Table 1. If a participant tests positive for HIV infection at baseline or at any follow-up visit, he will be withdrawn from this study and undergo counselling and referral to the HIV clinic of his choice. Participants who withdraw before or test positive at the month 1 visit will be replaced; replacement participants in the RCT will undergo randomization and not necessarily be assigned to the arm to which the participant they replace was assigned.

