Trial enrollment and randomization. Once consent has been given, participants will be randomized to a study arm. The process of randomization to one of two study arms will be explained carefully and reviewed as part of the informed consent process. Computer-generated randomization will be used to assign participants in a 1:1 ratio to the standard care or intervention group, in blocks of 4, to ensure that equal numbers are randomized across arms. Numbered envelopes indicating the assignment will be prepared in and sealed by the UW CFAR Biometrics Core; study staff will not be aware of an individual's condition until the envelope is opened.

Clinic visits. Consistent with the latest Kenyan guidelines, all trial field-test participants will undergo study procedures at baseline, month 1, month 3, and month 6 at the **Anza Mapema** clinic. As for the pilot study, clinic visits will include HIV counselling and testing, screening for STI symptoms, and individual counselling about HIV prevention methods, including standard of care counselling (information, risk reduction, and PrEP counselling). A standardized physical exam will be performed at each visit, and both blood and urine samples will be collected. For participants taking PrEP, medical history will also focus on PrEP side effects and seroconversion symptoms, and PrEP refills will be provided (monthly for the first 3 months then quarterly). After completing these procedures, RCT participants will complete a detailed ACASI described below. Each of the four clinic visits (baseline, month 1, month 3, and month 6) will take from 1.5 to 2 hours; participants will be reimbursed KSh 500 for each clinic visit.

Standard care. All participants will receive standard care at the *Anza Mapema* Clinic, including standard counseling as described above; screening for depressive symptoms and substance use disorder; monthly *Anza Mapema* peer outreach for education and supply of condoms and lubricants; support group meetings; and social events as described above under “Previous Studies and Rationale.” Attendance at *Anza Mapema* support groups and social events by *Shauriana* study participants will be tracked, as will the content of these group and social events during the study period. To ensure fidelity of delivery for each arm, we will review study progress, procedures, and emergent issues at weekly study meetings.

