Sexual identification	27-item lesbian, gay, and bisexual identity scale (LGBIS),  previously used in Kenya 	ACASI	Quarterly

Laboratory testing. HIV testing at screening and follow-up visits will be performed with two rapid tests (Determine®, Abbott Laboratories, Abbott Park, IL, USA; and First Response®, Premier Medical Corporation, Kachigam, Nani Daman, India), in accordance with the latest Kenyan HIV testing guidelines. Dried blood spots will be collected per an existing SOP at the

Anza Mapema Clinic, and stored for analysis of PrEP drug levels (i.e., detection of TFV-DP and FTC-TP), should funding permit. Safety monitoring in the RCT will be done at a higher standard than is currently available in Kenya, where costs of lab testing have prohibited routine baseline testing and instead use an approach targeted based on signs or symptoms of kidney or liver disease. Serum will be tested at baseline for creatinine level using the Cobas Integra 400 Plus biochemistry analyzer (Roche, Germany), to document normal renal function prior to PrEP start. Baseline serum will also be tested for hepatitis B surface antigen (HBsAg) using SD Bioline HBsAg WB at the CDC-KEMRI laboratory in Kisumu; men who do not have chronic hepatitis B (i.e., those who are HBsAg negative) will be offered hepatitis B vaccination.

Blood and urine aliquots from baseline, month 3, and month 6 will be stored at -80°C in the NRHS laboratory in Kisumu. Urine samples will be shipped on dry ice for testing utilizing the liquid chromatography tandem mass spectrometry (LC-MS/MS) urine tenofovir (TFV) assay developed at Philadelphia FIGHT/Children's Hospital of Philadelphia by [name] and colleagues, currently performed by Molecular Testing Labs in Vancouver, Washington, USA. This assay detects TFV with greater sensitivity than plasma-based measures, with a detection window within 7 days of the last TDF/FTC dose. In addition, dried blood spots will be shipped to Molecular Testing labs for TFV-DP and FTC-TP quantitation using LC-MS/MS to estimate the number of doses taken in the past 7 days. If any participant acquires HIV during the study, HIV-1 genotypic resistance testing will be conducted on stored samples at the CDC-KEMRI laboratory in Kisumu, to determine whether acquired virus is resistant to TDF or FTC.

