Collection of specimens is for study purposes (e.g., monitoring of outcomes), but results will also be used to provide appropriate clinical care (e.g., PrEP safety monitoring, HIV care referral if indicated). HIV testing using a finger-prick blood sample will be conducted at all study visits, regardless of PrEP uptake or adherence. This testing will be conducted following current Kenyan MoH guidelines. Safety monitoring in the RCT will be done at a higher standard than is currently available in Kenya, where costs of lab testing have prohibited routine baseline testing and instead use an approach targeted based on signs or symptoms of kidney or liver disease. Serum will be tested at baseline for creatinine level using the Cobas Integra 400 Plus biochemistry analyzer (Roche, Germany), to document normal renal function prior to PrEP start. Baseline serum will also be tested for HBsAg using SD Bioline HBsAg WB at the CDC-KEMRI laboratory in Kisumu; men who do not have chronic hepatitis B (i.e., HBsAg positive) will be offered hepatitis B vaccination.

Urine and dried blood spots will be collected and stored for assessment of PrEP drug levels at baseline, month 3, and month 6. Blood draws at the baseline, month 3, and month 6 visits will have a maximum volume of 15 mL, with up to 10 mL for required for laboratory testing and 5 mL to store for assessment of genotypic drug resistance for any participant who acquired HIV during the study. Consent will be obtained prior to all specimen collection.

**Recruitment of Subjects and Consent Procedures:** Subjects will be recruited by the NYARWEK team using existing peer networks, snowballing and venue-based referrals. All interested subjects will be referred to the *Anza Mapema* clinic for study eligibility screening, for which a brief screening consent will be used (Appendix C). If an individual is found to be eligible, he will undergo the informed consent process outlined below. Men who are found to be ineligible will be referred to HIV prevention or care programming as indicated, including risk reduction counseling, condoms and lubricants, STI screening and treatment, programmatic PrEP if eligible and interested, and HIV care for men who test positive. These men will receive KSh 350 for their time and transport to the clinic for the screening process.

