#### **14. Laboratory Specimens and Biohazard Containment:**

***Laboratory Specimens:*** The following specimens will be collected for the tests to be conducted for the randomized trial:

- Blood (15 milliliters) for creatinine and hepatitis B surface antigen testing at baseline and dried blood spots plus storage at baseline, month 3, and month 6
- Urine (10 milliliters) for PrEP drug level testing

Research staff will adhere to standards of good clinical laboratory practice, and local SOPs for specimen management, including proper collection, processing, labeling, and transport of specimens to the CDC-KEMRI laboratory for testing or the UNIM Research and Training Centre for storage.

***Biohazard Containment:*** Transmission of HIV and other blood borne pathogens can occur through contact with contaminated needles, blood, and blood products. Appropriate blood and secretion precautions will be employed by all personnel in the collection of clinical samples and the shipping and handling of all clinical samples and isolates for this study, as currently recommended by the World Health Organization and the Kenyan Ministry of Health. After all requisite permissions are obtained, urine and dried blood spot samples will be shipped to [name] at the University of Washington and then forwarded to Molecular Testing Labs in Vancouver, Washington, USA, for PrEP drug level testing. All specimens will be shipped using packaging that meets requirements specified by the International Air Transport Association Dangerous Good Regulations for UN 3373, Biological Substance, Category B, and Packing Instruction 650. In addition, all infectious specimens will be transported in accordance with United States regulations (42 CFR 72).

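### Resistance genotyping is promised on stored samples for any man who acquires HIV, but no blood is planned to be stored at or after a positive test at month 1

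*Combined protocol and SAP*

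**What the plan says.** **The commitment.** Section 11 (Aim 2, Laboratory testing) says that if a participant acquires HIV, "HIV-1 genotypic resistance testing will be conducted on stored samples at the CDC-KEMRI laboratory in Kisumu". The stated purpose is to learn whether the virus is resistant to either PrEP drug.

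**The stored material.** Three places give the same schedule:

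- Section 11, Laboratory testing: "Blood and urine aliquots from baseline, month 3, and month 6 will be stored at -80°C in the NRHS laboratory in Kisumu".
- Section 12, Research Material Obtained from Participants: "Blood draws at the baseline, month 3, and month 6 visits will have a maximum volume of 15 mL". That volume includes "5 mL to store for assessment of genotypic drug resistance for any participant who acquired HIV during the study".
- Section 14, Laboratory Specimens: "dried blood spots plus storage at baseline, month 3, and month 6".

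**HIV testing and what follows a positive result.** Section 12 has finger-prick HIV testing at every study visit. Section 11 (Aim 2, Clinic visits) sets those visits at baseline and months 1, 3 and 6. Section 11 (Recruitment) states: "If a participant tests positive for HIV infection at baseline or at any follow-up visit, he will be withdrawn from this study". It adds that a man who is positive at month 1 is replaced. At withdrawal the protocol describes an exit interview (Sections 11 and 12) and a withdrawal survey (Section 12), but no specimen.

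**The text that points the other way.** Section 11 (Aim 2, Clinic visits) says: "A standardized physical exam will be performed at each visit, and both blood and urine samples will be collected".

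**The concern.** The genotyping relies on stored blood, and the storage schedule omits one of the visits at which HIV is tested. A man found positive at month 1 leaves the study at that point and may choose any HIV clinic, so a later study sample cannot be assumed. The blood held for him predates his positive test.

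What is at stake is a safety observation. Section 12 lists acquisition of a resistant strain, when adherence is poor, among the risks of PrEP. Section 8 gives reason to expect poor adherence: in the earlier Kisumu PrEP cohort, drug levels were protective at only 28 of 275 visits (10.2%). A specimen not stored on the day cannot be recovered later.

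**Working it through.** **Step 1: compare the schedules.**

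| RCT visit | HIV test | Blood storage stated |
|---|---|---|
| Baseline | yes | yes |
| Month 1 | yes | no |
| Month 3 | yes | yes |
| Month 6 | yes | yes |

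Month 1 is the only scheduled HIV test without planned storage, and it is one of three follow-up tests. Men who test positive at month 3 or 6 are covered provided the tube is drawn before withdrawal.

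**Step 2: what the baseline aliquot can show.** It was taken when the man tested negative and before any PrEP start in the trial. If he was already infected but not yet detectable by rapid test, it may contain virus and could show resistance already present. It cannot show resistance that emerged afterwards on PrEP. If he was infected after baseline, it does not contain the virus in question.

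**Step 3: size of the gap.** Inputs: 60 men followed for 6 months (Section 11), and the earlier Kisumu cohort's incidence of about 2.3 per 100 person-years overall and about 4.6 among men reporting condomless anal intercourse at baseline (Section 8). Assumptions: these rates apply here, are constant, and are not reduced by PrEP.

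- Person-time to month 1: 60 × 1/12 = 5 person-years.
- Expected infections: 5 × 0.023 = 0.115 (0.12); 5 × 0.046 = 0.23.
- Chance of at least one: 1 − exp(−0.115) = 0.109 (11%); 1 − exp(−0.23) = 0.205 (about 21% before rounding to three places).
- Person-time over 6 months: 60 × 0.5 = 30 person-years.
- Expected infections over 6 months: 30 × 0.023 = 0.69; 30 × 0.046 = 1.38.
- Share falling in month 1: 5/30 = 17%.

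**Step 4: blood volume.** The 15 mL maximum in Section 12 is 10 mL for testing plus 5 mL for storage. A single 5 mL tube at month 1 is within that limit.

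**The case against.** The strongest counter-argument is the clinic-visit text in Section 11. Read literally, it has blood and urine collected at month 1, so a specimen may exist. Appendix G, the schedule of procedures, might settle this but was not available to check. This stands as a reason not to claim that no sample will exist. It does not close the gap: the sentence does not mention storage, and three other places confine storage to baseline and months 3 and 6. Table 2 likewise lists drug levels as quarterly while safety reports start at month 1.

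It is also fair that resistance is not a Table 2 outcome, that Section 13 plans no analysis of it, and that Section 12 regards PrEP risks as not truly risks of the research. This limits the consequence but does not cancel the commitment to genotype.

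A reader might infer more than the documents support:

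- *That genotyping is impossible for every month 1 positive.* A man already infected at baseline may have virus in his stored aliquot.
- *That undetected baseline infections raise the month 1 figure.* Recent infections missed at month 1 would surface at month 3; with a constant rate and the same detection delay, the two roughly cancel.
- *That the chance is 35% to 42%.* Those values come from applying 8.6 and 10.9 per 100 person-years, which Section 6 reports for a coastal cohort and for Nairobi male sex workers, not for Kisumu.
- *That most resistance data would be lost.* This could happen if the trial's only infection fell in month 1, but on average the share is 17%.
- *That positives at unscheduled visits are certainly affected.* Section 11 says such visits are documented; it does not say HIV is tested there.
- *That early seroconverters are those most likely to have started PrEP near infection.* Nothing supports this; PrEP uptake is itself an outcome.
- *That a promised drug level at seroconversion is lost.* None is promised.

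**Conclusion.** The point holds in a limited form. For a man who tests positive at month 1, the plan as written provides no stored sample at or after the positive test, so it does not secure the material for the genotyping it commits to. The clinic-visit text also conflicts with the storage schedule given in three other places.

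The likely number affected is zero or one man. The 11% to 21% chance rests on carrying the earlier Kisumu rates over unchanged with no PrEP effect; the upper figure treats every participant as having the rate seen in the 29% of that cohort who reported condomless anal intercourse. The acceptability, feasibility and safety outcomes listed in Table 2 and the between-arm comparisons are unaffected. The correction is still worth making because the commitment already exists, the loss would be permanent and the remedy is small.

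**What to change.** In Section 11 (Laboratory testing), Section 12 (Research Material Obtained from Participants) and Section 14 (Laboratory Specimens), state that at any visit with a positive HIV test, including month 1, the existing 5 mL storage tube is drawn with consent and stored before withdrawal is processed, for the genotyping in Section 11. A urine aliquot could optionally be stored at the same time.

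Reconcile the clinic-visit text in Section 11 with the storage schedule by saying what is collected at month 1 and whether it is kept. Check that Appendix G and the RCT consent agree.

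The cost is one added protocol and consent sentence, and one tube for an expected zero or one man at month 1, with no new assay. The downside is a blood draw on the day of diagnosis, which he may decline.

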reviewed by the team and discussed at weekly meetings. At the conclusion of the pilot study, we will assess whether we need to revise the intervention based on pilot test findings. If this is the case, we will submit revisions to the ethical review board at Maseno University and to the human subjects research committee at the University of Washington for approval.

**Aim 2 Procedures: RCT of the Shauriana Intervention.** Aim 2 work will use an RCT design to test the acceptability, feasibility, and safety of the **Shauriana** Intervention compared to standard care and estimate initial effect size. Acceptability will be assessed using Likert scales in participant ACASI questionnaires and qualitative exit interviews with participants in each study arm. Feasibility will be assessed at regular research team and peer facilitator meetings, which will be minuted. Safety will be assessed through careful monitoring of study participants to identify and report any adverse events. Information on perceived or experienced social harms and benefits will be collected by study staff at all clinic visits and assessed in greater depth in qualitative exit interviews. Additional trial outcomes that will be monitored and reported include screening and enrollment numbers, visit and intervention attendance, overall retention, and self-reported PrEP uptake and adherence. At the end of the trial, urine samples will be tested for tenofovir (TFV) drug levels (see Laboratory details, below). Dried blood spots will also be collected and stored for future testing of TFV-DP and FTC-TP levels, should funding permit.

Recruitment. The **Shauriana** Intervention pilot RCT will enroll 60 HIV-negative men (30 in the intervention and 30 in SOC) and follow participants for 6 months. We will recruit 60 participants over the course of 3 months; this target is realistic, given enrolment of over 160 men in the **Anza Mapema PrEP** cohort within a 2-month period. Potentially eligible participants will be recruited by NYARWEK, then referred to the **Anza Mapema** Clinic for screening and consenting, as described on pp. 11-12.

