ACASI measures and data collection. Due to its enhanced privacy, ACASI will be the main method of data collection, in English, Dholuo, or Kiswahili. This method was successfully used in the *Anza Mapema* project. Because participants occasionally have difficulties using ACASI, a research assistant will be available to assist participants if needed. The Anza Mapema clinic has an ACASI in use that includes questions on sociodemographics, sexual history, risk behavior, intimate partner violence, depressive symptoms, alcohol and other substance use, trauma, HIV risk perception, and awareness and use of PrEP and post-exposure prophylaxis for HIV prevention. Data elements that have been added to the ACASI specifically for the *Shauriana* study are listed below in Table 2. Our selection of measures for the *Shauriana* ACASI has drawn from our conceptual model for the *Shikamana* intervention and from the qualitative and intervention development work completed in protocol

MSU/DRPI/MUERC/00637/18. The *Shauriana* ACASI will be updated after the Aim 1 pilot test, balancing the need for data collection with the need to ensure a reasonable ACASI length without undue burden on participants. The final ACASI questionnaire is included in “Appendix F: Shauriana ACASI.”

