**Table 2. PrEP-oriented and *Shauriana*-Specific Data Elements for Collection by ACASI**

Data Element	Content	Method	Frequency
Primary Outcome Variables			
Acceptability	5-point Likert scales evaluating acceptability of the Shauriana intervention components,  exit interviews for detailed qualitative feedback	ACASI, exit interviews	Quarterly
Feasibility	Visit attendance, session delivery, documentation of peer contacts, minutes of research team meetings	Clinic and intervention data, minutes	Ongoing
Safety	Adverse events reported by participants or study staff; self-reported consequences of study participation in exit interviews	Reports at clinic visits, exit interviews	M1 then quarterly
Secondary Outcome Variables			
PrEP uptake	Two questions on past and ongoing PrEP use	ACASI	Quarterly
PrEP adherence	A series of self-report measures we have used in previous work.	ACASI	Quarterly
PrEP refills	Documented at Anza Mapema for each participant	Clinic data	Quarterly
PrEP drug levels	Urine TFV levels  DBS TFV-DP and FTC-TP levels (if funding permits)	Laboratory	Quarterly
Potential Correlates of Retention and Adherence			
Risk perception	A question on the participant’s self-assessment of his chance of getting HIV/AIDS	ACASI	Quarterly
PrEP knowledge	PrEP knowledge questions (based on relevant literature and completed qualitative research by the team)	ACASI	Quarterly
Motivation/skills	LifeWindows Information-Motivation-Behavioral Skills adherence questionnaire,  adapted for PrEP use based on completed qualitative research by the team.	ACASI	Quarterly
PrEP distrust	PrEP-related distrust, skepticism, trust in providers, and ownership (championing) per [name] et al. 	ACASI	Quarterly
Shared decision making	Participant-reported sharing of decision-making related to PrEP; adapted from Barr et al. 	ACASI	Quarterly
Social support and loneliness	Multidimensional Scale of Perceived Social Support, a 12-item scale of perceived support from family, friends, others 	ACASI	Quarterly
Self-esteem	10-item Rosenberg self-esteem scale,  previously used in this population 	ACASI	Quarterly
Resilience	Coping self-efficacy scale: 13-item version validated in HIV+ GBMSM with depressed mood 	ACASI	Quarterly

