Exit interviews. At study completion or any visit on which a participant withdraws, an exit interview will be conducted regarding experiences, including any social harms of participation and feedback on standard care or the *Shauriana* intervention. Exit interviews will be conducted by the *Shauriana* Project Research Coordinator, who is based at NYARWEK, using a semi-structured exit interview guide. Notes will be taken and interviews will be recorded using a digital recorder. All participants who complete an exit interview will receive KSh 500 as reimbursement for their time and transport. The topic guide for the exit interviews is included in “[Appendix E: Shauriana Exit Interview Guide](#).”

Schedule of procedures. A table summarizing procedures for the Shauriana study is included in “[Appendix G: Schedule of Procedures](#).”

Power considerations. This project is designed to develop a novel intervention to promote PrEP adherence and sexual health among African GBMSM and to assess its acceptability, feasibility, and safety in a clinical trial setting. It is not designed or powered to determine the overall intervention effect nor the effects of individual components of the intervention. Data on PrEP drug levels and other secondary outcomes in each study arm will help to evaluate whether the intervention is at least as good as standard care and provide some insight into the promise of the intervention to inform larger-scale testing. See Section 13 for statistical analysis plans.

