The risk for loss of privacy will be minimized by strict confidentiality procedures. Identifying information collected for tracing purposes will be kept in an encrypted contact information file on a password-protected laptop computer with an encrypted hard drive. A master electronic file including the linkage of names to numbers (used to identify participants who return without a numbered study card) will be encrypted and retained on a single computer at NRHS in a secure location. This master file will be checked each day for duplicates. Consents will be stored in a separate area in a locked file cabinet. All personal identifying information will be destroyed immediately after the study is completed. In addition, privacy will be protected by ensuring that computer-assisted interviews and examinations take place in private rooms. Recordings from pilot test intervention sessions and participant interviews will be transcribed and stored on a password-protected personal computer. Interviews conducted in Swahili or Dholuo will be simultaneously translated into English and transcribed, with back-translation and verification by a different person to ensure accuracy. Participants will not be identified by name in the interview transcripts, rather by study ID. We will also protect privacy by developing individualized procedures for study-related contacts in collaboration with each participant. NRHS study staff and peer outreach workers already have 2-10 years of experience maintaining confidentiality and privacy with GBMSM in Kisumu, and are either from the GBMSM community or face social challenges due to secondary stigma. The NYARWEK research team, including all peer facilitators, similarly have all been trained in human subjects research protections and privacy protections. All newly hired staff and peers will undergo rigorous training on the protection of confidentiality and particular need for discretion in working with this population, whether in the clinic or community.

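### Exit interviews, one source for primary acceptability and safety, are run from the organisation whose peers deliver the intervention, and Table 2 lists no private self-completed source for harms of participation

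*Combined protocol and SAP*

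**What the plan says.** Section 11, under Exit interviews, assigns all RCT exit interviews to the Shauriana "Project Research Coordinator, who is based at NYARWEK, using a semi-structured exit interview guide". The interview covers experiences in the study, "including any social harms of participation and feedback on standard care or the" Shauriana intervention.

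Table 2 has three primary outcomes: acceptability, feasibility and safety. The interview feeds two of them. For acceptability it adds "exit interviews for detailed qualitative feedback" to the Likert scales. For safety it supplies "self-reported consequences of study participation in exit interviews", alongside adverse events reported at clinic visits.

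NYARWEK's role is described in several places. Section 12 (Adequacy of Protection from Risks) refers to "The NYARWEK research team, including all peer facilitators". Section 11 (Recruitment) has interested men given the card of "the NYARWEK peer facilitator they were in contact with". Section 11 (Study Sites) makes NYARWEK and its member organisations' premises places of delivery.

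Two other provisions matter. Section 11 (Aim 2 Procedures) states: "Information on perceived or experienced social harms and benefits will be collected by study staff at all clinic visits". Section 11 (ACASI measures and data collection) gives the reason for self-interview: "Due to its enhanced privacy, ACASI will be the main method of data collection".

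**The concern.** A man who had trouble with his facilitator is asked about it, in person, by someone from the facilitator's own organisation. He may soften criticism or leave it out. The expected direction is higher praise for the intervention and fewer recorded harms. It would act mainly in the intervention arm, because standard-care men have no assigned facilitator.

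Harm of this kind is foreseeable on the plan's own account. Section 12 lists loss of privacy through contact with peers among the risks of taking part, and the pilot description in Section 11 gives unintended disclosure and breached confidentiality as examples of social harm.

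What is at stake is the statement that the intervention is acceptable and safe. Section 13 tallies social harms by arm and uses the interviews to weigh the intervention against standard care. With 30 men per arm, one or two unreported events could change how that tally reads.

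**Working it through.** The plan gives no figure for interviewer effects, so there is none to reproduce. The check is mainly a comparison of sources.

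**Which results pass through this interviewer**

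| Result | Source | Through the NYARWEK-based interviewer? |
|---|---|---|
| Acceptability, Mann-Whitney test at months 3 and 6 (Section 13) | ACASI Likert scores | No |
| Acceptability, qualitative (Section 13) | Exit interviews | Yes |
| Harms at clinic visits (Section 11, Aim 2; Table 2) | Asked by study staff at the Anza Mapema Clinic | No, but elicited by staff |
| Harms at exit (Table 2; Section 11) | Exit interviews | Yes |
| Harms by private self-completion | None listed in the Table 2 safety row | Not applicable |

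The exposure is therefore confined to the qualitative acceptability findings and the exit-interview share of the harms data.

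**Whether anything else covers the gap.** The ACASI described in Sections 11 and 12 asks about violence, trauma, stigma and discrimination. As described, these items do not ask whether an event arose from taking part in the study. Recording of intervention sessions is limited to the pilot (Section 12), so RCT recordings cannot show facilitator problems. Section 15 discusses contamination and unequal attention but not interviewer effects. The ACASI questionnaire (Appendix F) and interview guide (Appendix E) are not in the supplied text, so the gap is established for Table 2 and the narrative only.

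**Illustration of scale.** All rates here are assumptions.

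- Suppose 3 of 30 intervention men (3/30 = 10%) have a facilitator-related harm, and each independently withholds it from the interviewer with probability *w*.
- Expected number recorded = 3 × (1 − *w*). P(none recorded) = *w*³.
- *w* = 0.5: expected 3 × 0.5 = 1.5 (1.5/30 = 5%); P(none) = 0.5³ = 12.5%.
- *w* = 0.7: expected 3 × 0.3 = 0.9 (0.9/30 = 3%); P(none) = 0.7³ = 34.3%.

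These figures cover the interview alone. Now add one clinic-visit route with the same withholding rate.

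- If the two routes are independent, each harm is missed by both with probability *w*². P(none) is then (0.5²)³ = 0.25³ = 1.6%, or (0.7²)³ = 0.49³ = 11.8%.
- If a man who withholds from one asker always withholds from the other, the second route adds nothing and the figures stay at 12.5% and 34.3%.

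Under these assumed inputs the two routes together lie between 1.6% and 12.5%, or between 11.8% and 34.3%. The position within each range depends on how alike the two routes are. Both require telling a member of staff, which is the reason for adding a route that does not.

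**The case against.** The strongest reply is that the protocol already has a harms route outside NYARWEK. Study staff ask at every clinic visit, at Anza Mapema, with the exit interview added for depth. Men who withdraw also get a survey of their reasons (Section 12). A community advisory board helps monitor social harm; it includes NYARWEK's Executive Director, but also a lawyer, a religious leader and a district health officer. This stands. A reader might infer that a harmed man can report only to his facilitator's organisation, and the documents do not support that.

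A reader might also infer that the interviewer has a personal stake, or that the primary acceptability result is biased. Neither is supported. The text says only where the coordinator is based. It does not say that the coordinator delivers sessions or supervises peers. The Mann-Whitney comparison uses ACASI scores. Any interviewer would know the arm, because the questions ask about the care received.

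Moving the interviews to clinic staff is not a clean remedy. Anza Mapema provides the standard care that control men would be asked to judge, so the affiliation problem would move to the other arm. Section 7 notes that HIV care providers are often not affirming of these men, and community interviewers trained through NYARWEK drew out criticism of providers and peers in the earlier qualitative work (Section 8). That work did not concern NYARWEK's own intervention, but it shows that a community interviewer can have advantages.

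Nor does private self-completion guarantee candour. In the Anza Mapema PrEP cohort men reported taking PrEP most or all of the time at 89% of visits, while 64.7% of visits had no detectable drug. That is adherence rather than harm, and Section 8 does not say how the self-reports were taken.

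What remains is that both listed harms routes depend on disclosure to staff, and that the limitations do not mention the interviewer's affiliation.

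**Conclusion.** The point holds as a risk of bias, limited in extent. It concerns the qualitative acceptability findings and the exit-interview part of the safety data. The direction, more praise and fewer facilitator-related harms in the intervention arm, is a methodological inference from organisational affiliation. The documents contain no evidence that bias occurs and no basis for estimating its size. The 12.5% and 34% figures rest on assumed harm and withholding rates for one route and should not be read as the chance that the trial misses harms.

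The more useful finding is the missing source. The protocol chooses ACASI for its privacy, yet the safety row of Table 2 does not use it. This conclusion assumes that Appendix F has no items on harms attributed to participation. If it has, the change reduces to naming ACASI in Table 2 and tallying by source.

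**What to change.** 1. Add a short structured block on social harms of participation to the ACASI at months 1, 3 and 6 in both arms. It could cover unintended disclosure, breach of confidentiality, and problems with staff or peers. This matches the month 1 then quarterly timing of the safety row, and Section 11 already has men complete the ACASI at those visits.
2. Add ACASI to the Method column of the Table 2 safety row.
3. In Section 13, tally harms by arm and by source: ACASI, clinic-visit report, exit interview. This is in addition to adverse event reports and does not replace them.
4. Keep the exit interview for qualitative depth, and state the interviewer's affiliation as a limitation in Section 15 and in the trial report.
5. Optionally, change the interviewer. If so, use existing research staff who deliver neither the intervention nor standard-care counselling. This is a trade-off, because some men may be more at ease with a community interviewer.

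The cost is a few ACASI items and a slightly longer questionnaire. Items 1 to 4 need no new staff or visits.
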